6. MEASUREMENT

6.1 Schedule of Measurement

Patients will be followed until 30 days after the initial platelet transfusion, until they have not received a platelet transfusion for 10 days after the most recent platelet transfusion (assumed to have had platelet recovery), or until hospital discharge, whichever comes first. Patients will be studied during only one episode of thrombocytopenia.

The following is a list of the data that will be collected while the patient is on study. Table 1 outlines the schedule of laboratory assessments.

At Baseline:

- 1. Demographics and Medical History:
 - Weight
 - Height
 - Date of birth
 - Gender
 - Ethnic origin
 - Race
 - Any prior pregnancies (*Yes give #, or No*)
 - Any prior transfusions (Yes or No)
 - Diagnosis (disease and type of treatment; i.e., chemotherapy or type of hemopoietic transplant)
 - ABO type of patient
 - If receiving allogeneic transplant, ABO type of donor and whether donor is related (*Yes or No*),
 - Type and date of transplant, if any
- 2. Laboratory:
 - Platelet count
 - Hematocrit / Hemoglobin
 - PT, INR, PTT and Fibrinogen
 - HLA antibody screen
- 3. Hemostatic Assessment:
 - Assessment of bleeding by study personnel will be performed by means of physical assessment of the patient, patient interview (if possible) and review of patient chart and laboratory data. Research staff will perform the physical assessment and interview of the patient before reviewing the patient's chart and laboratory data to allow an objective patient assessment without the bias that

might be introduced by doing the chart and laboratory data reviews first. Research staff will perform the Hemostatic Assessment daily at approximately the same time each day.

Daily:

- 1. Laboratory:
 - Platelet count
 - Hematocrit / Hemoglobin
 - PT, INR, PTT and Fibrinogen if available as part of routine care
- 2. Hemostatic Assessment:
 - Research staff will perform the Hemostatic Assessment daily at approximately the same time each day. (See above)
- 3. Medications:
 - Anti-thrombotic and Fibrinolytic Inhibitor medications (name, dose, date started), if patient started either type of medication while on the study.

End of Study:

- 1. Laboratory:
 - Platelet count
 - Hematocrit / Hemoglobin
 - HLA antibody screen
 - PT, INR, PTT and Fibrinogen if available as part of routine care
- 2. Hemostatic Assessment (See above.)

With Each Platelet and Granulocyte Transfusion:

- Type of product transfused (granulocytes, apheresis platelets, pooled whole-bloodderived platelets, HLA or crossmatch compatible platelets)
- ABO type of the transfused platelets
- Platelets leukoreduced (Yes or No)
- Platelets volume reduced (Yes or No)
- Age of the apheresis platelets, or of pooled platelets if all same age
- Platelet count of platelets or granulocytes prepared for transfusion (at collection and issue if apheresis, at issue if whole-blood-derived platelets or granulocytes)
- Volume at issue of platelets or granulocytes transfused
- Post-transfusion platelet count between 10 minutes and 4 hours after each transfusion.

Tests for HLA and Platelet Specific Antibodies:

• With the development of suspected platelet refractoriness, a sample will be drawn for HLA antibody screening. Blood can also be drawn and tested for platelet specific antibodies depending on local practice. These tests will be considered part of routine patient care.

TEST	Baseline	Daily	End of Study	Transfusion	Other
Hemoglobin	R	R	R		
Hematocrit	R	R	R		
Platelet Count	R	R	R	R (post)	S*
Lymphocytotoxic Antibody Screen	R		R		R (if refractory)
PT and INR	R	S	S		
PTT	R	S	S		
Fibrinogen	R	S	S		
ABO RH Typing	R				

 Table 1: Schedule of Patient Laboratory Assessments

R = required

S = lab results collected if available (done as part of patient standard care).

*Additional platelet counts will be collected if ordered by the treating physician (for active bleeding or invasive procedure)

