3. STUDY POPULATION

3.1 Inclusion Criteria

- 1. Patients with, or expected to have, hypoproliferative thrombocytopenia who are expected to have a platelet count of $\leq 10,000 \mu l$ for ≥ 5 days, and be in the hospital for ≥ 5 days.
- 2. Weight between 10 and 135 kilograms.
- 3. Patients whose PT/INR, PTT and fibrinogen assays, measured within 72 hours before study entry, are as follows:
 - a) $PT \le 1.3 X$ upper limit of normal for the laboratory
 - b) PTT \leq 1.3 X upper limit of normal for the laboratory
 - c) Fibrinogen $\geq 100 \text{mg/dL}$
- 4. Patients with any diagnosis undergoing or with completed hematopoietic stem cell transplantation, and patients with a diagnosis of acute or chronic leukemia, non-Hodgkins and Hodgkins lymphoma, myeloma, myelodysplasia, or non-hematologic malignancy undergoing or with completed chemotherapy.
- 5. During this hospitalization, the patient has not yet received any platelet transfusions related to the current or planned course of therapy. Individual platelet transfusions given prior to the study and unrelated to thrombocytopenia will not exclude the patient.

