8. STATISTICAL CONSIDERATIONS

8.1 Analysis Plan

The primary analysis for the primary endpoint, the percentage of patients with at least one episode of Grade 2 or higher bleeding, will be three one-degree-of-freedom chi-square tests, each comparing a pair of treatment groups. These tests will be carried out at the .017 significance level to adjust for the multiple comparisons.

These analyses will be done on an intention-to-treat basis. That is, patients will be counted in the treatment arm to which they were randomly assigned, even if they actually received transfusions that were not according to their assigned dosing strategy. Any such "crossovers" between treatment arms will tend to make the observed percentages of patients with Grade 2 or higher bleeding more similar between treatment arms than they would have been if all patients had been treated according to their assigned dosing strategy. Thus, an intention-to-treat analysis is conservative.

The most important secondary endpoints, capturing key data on costs and safety, are the total number of platelets dispensed, the total number of transfusion events, the highest grade of bleeding, and the bleeding severity score (if such a score has been validated and published by the end of the Platelet Dose trial, and the necessary information to calculate the score was collected). These endpoints capture the main components of transfusion costs and seriousness of bleeding. Differences between each pair of treatment arms for these three or four pre-specified key secondary outcomes will be tested, each at the .017 significance level, also on an intention-to-treat basis. For other secondary outcomes, only descriptive data will be presented.

Platelet usage, number of transfusion events, and the severity score (if continuous) are expected to have highly skewed distributions, so for these endpoints a log transform (or other suitable transform) will be carried out before using a t-test to compare treatment arms. If no acceptable transform can be found, a Wilcoxon rank sum test will be used instead of the t-test.

In the analysis of highest grade of bleeding, some grades are expected to be quite rare. Proc StatXact will be used for each of the 2x4 tables to obtain precise Monte-Carlo estimates of the p-value for an exact Kruskall-Wallis test for treatment differences, where the bleeding grades are considered ordered. If the severity score is ordinal, similar analyses will be carried out for that outcome.

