8.2 Sample Size and Power

The primary endpoint for the study is the percentage of patients with at least one episode of bleeding at Grade 2 or higher, as determined by the Platelet Dose Trial Bleeding Scale.

Eighty-five percent power was desired to detect an absolute difference of 12.5% between any pair of dose strategies. The estimated percentage of patients who will experience Grade 2 or higher bleeding is 50%. Sample size for a chi-square test at the .017 level was calculated for a scenario with true percentages of 43.75% and 56.25%, assuming an interim monitoring plan with three interim looks and one final look. (See section 7.2.) Without taking into account loss to follow-up, 389 patients per arm (1167 patients in all) would be needed to achieve 85% power. This sample size would also provide 80% power to detect a treatment arm difference if the true percentages were 44.1% and 55.9% (an absolute difference of 11.8%) and 90% power to detect a treatment arm difference if the true percentages were 43.3% and 56.7% (an absolute difference of 13.4%). A sample size of 445 per arm would be needed for 90% power to detect a difference with true percentages of 43.75% and 56.25%.

Because the patients in this study will be hospitalized, loss to follow-up is expected to be no more than 10%. Conservatively allowing for 13.5% loss to follow-up, the target sample size is 450 patients per arm (1350 patients in all).

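### The primary analysis and bleeding window are not tied to the first platelet transfusion, so patients and days without dose exposure dilute the dose contrast, and section 8.2 makes no allowance for this

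*Protocol*

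**What the plan says.** Entry: section 3.1 opens with "Patients with, or expected to have, hypoproliferative thrombocytopenia who are expected to have a platelet count of" a stated level for a stated time. An expectation is therefore enough, and the patient must not yet have had platelets for the current or planned course. Section 4.3 randomises at enrolment.

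Analysis: the primary test in section 8.1 is "three one-degree-of-freedom chi-square tests, each comparing a pair of treatment groups". On the population it says "These analyses will be done on an intention-to-treat basis", with patients kept in the assigned arm. It mentions dilution only from crossovers, and calls the result conservative.

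Observation: section 6.4 has bleeding assessed daily over the study period and does not tie the start to a transfusion. Section 6.1 sets the end: "Patients will be followed until 30 days after the initial platelet transfusion, until they have not received a platelet transfusion for 10 days" since the latest one, or until discharge, whichever comes first.

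Size: section 8.2 states "Eighty-five percent power was desired to detect an absolute difference of 12.5% between any pair of dose strategies". It needs 389 per arm before losses and raises this to 450 for 13.5% loss to follow-up. There is no other allowance.

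**The concern.** The assigned dose can act only once platelets are given. A patient who never reaches the trigger gets no study dose, yet counts in the primary comparison. The endpoint is any Grade 2 or higher bleeding, so one such bleed between randomisation and the first transfusion fixes a patient's outcome before dose can matter. That interval may not be short: section 5.3 expects most platelets in the second and third weeks after chemotherapy, while section 3.1 accepts patients still undergoing it.

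Both groups have the same expected bleeding rate in every arm, so they shrink each pairwise difference. The trial asks whether fewer platelets are safe, and a finding of little difference would support the lower dose. Dilution therefore works in the unsafe direction, and the remark in section 8.1 that intention to treat is conservative does not carry over.

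Separately, two of the three end-of-follow-up limits in section 6.1 have no start date for a never-transfused patient.

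**Working it through.** **Inputs.** Two-sided alpha 0.017 per pair (section 8.1); rates 43.75% and 56.25%, and four looks in all (both section 8.2); Lan-DeMets O'Brien-Fleming type spending (section 7.4.1). Evaluable patients per arm: 389 (13.5% loss), 450 × 0.90 = 405 (the 10% loss that section 8.2 gives as the most it expects), and 450 (no loss). The unexposed share f is **an assumption**; 5, 10 and 15% are shown.

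**Reproducing the plan.** With looks at 25, 50, 75 and 100% of information, the boundaries are z = 5.13, 3.54, 2.83 and 2.42, or p < 0.0001, 0.0004, 0.0046 and 0.0155, as in Table 5. The group-sequential calculation needs 378 per arm for 85% power, within 3% of 389; a fixed design needs 374, or 390 with continuity correction. Power at 389 comes out at 86.2% against the stated 85%. 389 / 0.865 = 449.7, giving 450 as stated.

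**Dilution model.** If a share f has the same event rate in all arms, the all-randomised difference is (1 − f) × 12.5 points: 11.9, 11.25 and 10.6 points at f = 5, 10 and 15%. Power is the probability, summed over the four looks, of crossing the boundaries with drift equal to the difference over its standard error. For transfused patients only, the difference stays at 12.5 points and the number per arm becomes N(1 − f).

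| f | All randomised, 389 | All randomised, 405 | All randomised, 450 | Transfused only, from 405 |
|---|---|---|---|---|
| 0% | 86.2% | 87.7% | 91.2% | 87.7% |
| 5% | 81.9% | 83.7% | 87.8% | 85.8% |
| 10% | 77.0% | 78.9% | 83.5% | 83.6% |
| 15% | 71.3% | 73.3% | 78.4% | 81.1% |

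Hand check at 405 and f = 10%, final look alone, rates 44.375% and 55.625%: null standard error √(0.5/405) = 0.0351, alternative 0.0349; (0.1125 − 2.42 × 0.0351)/0.0349 ≈ 0.79, so about 78.4%. The interim looks add the small remainder.

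**Break-even.** All-randomised power passes below 85% at f of about 1.5% (389), 3.4% (405) and 8.4% (450). These values hardly change when the event rate in the unexposed runs from 0 to 50%. If the protocol's 389 is instead taken as giving exactly 85%, then f = 1 − √(389/N): 0% at 389, 2.0% at 405 and 7.0% at 450.

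**Enrolment per arm for 85% power at 13.5% loss.** All randomised, 389/(1 − f)²/0.865: about 499, 556 and 623 at f = 5, 10 and 15%. Transfused only, 389/(1 − f)/0.865: about 474, 500 and 530.

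**Limit of the model.** The transfused-only column removes the whole share f. That fits the never-transfused. It is approximate for patients who bleed before a first transfusion, since they stay in the set and only their earlier bleeding days drop out.

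**The case against.** A reader might infer that the trial is underpowered. The protocol does not support that. It gives no value for f. It states the 12.5 points as a difference between dose strategies, which can be read as already covering all randomised patients; on that reading there is no shortfall. The entry criteria should keep f small: section 3.1 expects a count at or below the trigger for at least 5 days, and section 3.2 excludes Grade 2 or higher bleeding at screening. At 450 evaluable, f = 5% still leaves 87.8%. All of this stands, and it makes the power statement conditional.

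A reader might also infer that follow-up never ends for a never-transfused patient, or overruns a 30-day cap. Discharge does end it, and the 30 days run from the first transfusion, so they never limited time from enrolment for anyone. The gap is narrower: two of the three limits do not apply.

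The protocol does not say in terms that bleeding before the first transfusion counts. That follows from the intention-to-treat wording and the undivided study period. A statistical analysis plan, not shown, could refine it, but sections 6.1 and 8.1 already fix the follow-up clock and the population.

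Finally, intention to treat is standard, section 8.1 already plans a secondary per-protocol analysis, and restricting to transfused patients is a choice with its own risk. It would be too strong to say that such selection cannot depend on arm. The trigger is common, and neither arm nor dose is given to care staff, but the transfusion service knows the target dose. Under sections 5.2 and 5.3 a first transfusion may also be given for bleeding or a procedure.

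**Conclusion.** The point holds as a weakness in how the population, bleeding window and follow-up are fixed. Patients and days without dose exposure enter the primary analysis, they move the arms together, and section 8.2 does not allow for them.

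The size depends on two assumptions: that the 12.5 points is the effect in dose-exposed patients, and the value of f. Under the first, with 405 evaluable per arm, analysing transfused patients rather than all randomised gains about 2, 5 and 8 points of power at f = 5, 10 and 15%. A fall below 85% is possible at small f but is not shown. The restriction does not by itself restore 85% at the larger values of f. The change is worth making because it is cheap and the dilution favours a finding of no difference.

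**What to change.** - Section 8.1: define the primary set as all randomised patients with at least one platelet transfusion, analysed in the assigned arm, with Grade 2 or higher bleeding counted from the first transfusion.
- State how a bleed that prompts or spans the first transfusion is counted.
- Report the number never transfused by arm, and keep the all-randomised analysis as a prespecified sensitivity analysis.
- Section 6.1: state when observation ends if no transfusion is given.
- Section 8.2: say which population the 12.5 points refers to, and restate power over a range of f.

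The cost is wording in three sections and no new data; enrolment changes only if the restated power is judged too low. The downside is a departure from strict intention to treat. Selection is expected, not guaranteed, to be independent of arm, so the by-arm counts and the sensitivity analysis are needed. The change should be made before any results by arm are seen.

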6.2 Specimen Collection Procedures

Blood specimens will be collected from either a peripheral venipuncture site or central line using sterile technique. Specimens for coagulation tests will be drawn from peripheral sites whenever possible. A central line may be used if special procedures are in place to prevent compromise of coagulation study results. Specimens must be labeled with name and unique identifier as per institutional policies. Approximately 0.5mL to 10mL (capillary and pediatric specimens in pediatric "bullets") of blood will be collected at baseline and daily from patients for study laboratory assessments. After each transfusion, 0.5mL to 5mL of blood will be collected for a post transfusion platelet count. At the start of the study, an additional 2mL (pediatric patients) to 10mL of blood will be taken for ABO RH typing and/or a pregnancy test if necessary. At the end of the study, approximately 2mL (pediatric patients) to 10mL of blood will be blood will be blood will be drawn for final study laboratory assessments.

6.3 Definitions – Bleeding Scale

Table 2 describes the criteria that will be used to evaluate and grade bleeding.

 Table 2: Platelet Dose Trial Bleeding Scale

	Grade 1	Grade 2	Grade 3
Oral and nasal	 > Oropharyngeal bleeding – total duration of all episodes in previous 24 hours ≤ 30 minutes* > Petechiae of oral mucosa > Epistaxis – total duration of all episodes in previous 24 hours ≤ 30 minutes* 	 Oropharyngeal bleeding – total duration of all episodes in previous 24 hours > 30 minutes* Epistaxis – total duration of all episodes in previous 24 hours > 30 minutes* 	 Any bleeding requiring RBC transfusion over routine transfusion needs**
Skin, soft tissue, musculoskeletal	 > Petechiae of skin > Purpura ≤ 1 inch diameter > One or more spontaneous hematomas in the soft tissue or muscle > 1" 	 Purpura > 1 inch diameter Spontaneous hematoma in deeper tissues Joint bleeding (confirmed by aspiration, imaging study or other accepted technique) 	 Any bleeding requiring RBC transfusion over routine transfusion needs**
Gastrointestinal	Positive stool occult blood test	 Melanotic stool Hematochezia – visible red blood mixed in stool, not requiring a transfusion Hematemesis – Grossly visible blood in emesis or in nasogastric drainage tube (not related or secondary to swallowed blood) 	 Any bleeding requiring RBC transfusion over routine transfusion needs**
Genitourinary	 Any biochemical or microscopic Hb/RBCs without red urine Abnormal vaginal bleeding (Unexpected bleeding out of normal cycle OR Bleeding heavier than normal OR Breakthrough bleeding (patient on hormonal therapy to prevent bleeding)) with spotting 	 Gross/visible hematuria without need for transfusion Abnormal vaginal bleeding (Unexpected bleeding out of normal cycle OR Bleeding heavier than normal OR Breakthrough bleeding (patient on hormonal therapy to prevent bleeding)) more than spotting 	 Any bleeding requiring RBC transfusion over routine transfusion needs**
Pulmonary		 Hemoptysis – Visible blood Blood in broncho-pulmonary lavage, or blood tinged sputum (excluding those with nose or oropharyngeal bleeding) 	 Any bleeding requiring RBC transfusion over routine transfusion needs**

	Grade 1	Grade 2	Grade 3
Body Cavity		 Visible blood in body cavity fluid (e.g. red cells apparent in fluid aspirate) short of criteria for Grade 3 or 4 	Grossly bloody body cavity fluids and organ dysfunction with symptoms, and/or need to intervene (e.g. to aspirate), and/or need for transfusion
Central Nervous System		 Retinal bleeding without visual impairment Lumbar puncture with blood (>5 RBC/µL in CSF on microscopic analysis and non-traumatic tap), no symptoms and no visible red color 	 Lumbar puncture with visible red color in absence of symptoms, and non-traumatic tap
Invasive Sites		Bleeding at invasive sites (venipuncture sites, intravenous lines or catheter exit sites): active oozing at site for a cumulative total of > 1 hour in the previous 24 hours	 Any bleeding requiring RBC transfusion over routine transfusion needs**
Hemodynamic Instability			 Any bleeding associated with moderate hemodynamic instability (hypotension; >30mmHg fall or >30% decrease in either systolic or diastolic blood pressure) and requiring RBC transfusion over routine transfusion needs**

*Count actual bleeding (i.e. "running out" or need for basin, Kleenex, towel, etc.) not minor bleeding

**Red cell transfusion must be specifically related to treatment of bleeding within 24 hours of onset of bleeding

GRADE 4:

- Any bleeding associated with severe hemodynamic instability (hypotension; >50mm/Hg fall or >50% decrease in either systolic or diastolic blood pressure, with associated tachycardia (heart rate increase of ≥ 20% for 20 minutes) and requiring RBC transfusion over routine transfusion needs
- Fatal bleeding from any source
- Retinal bleeding with visual impairment (Visual impairment is defined as a field deficit, and patients with suspected visual impairment require an ophthalmologic consult for documentation)
- CNS symptoms with non-traumatic bloody lumbar puncture
- CNS bleeding on imaging study with or without dysfunction

6.4 Assessment and Adjudication Procedures

The persons performing the hemostatic assessments will not be informed of the patient's treatment group. However, great care must be taken to ensure that these assessments are performed in a standardized manner across all sites. Training of staff will be documented. Patients will be assessed for bleeding daily during the study period. Assessment findings will be recorded on the appropriate case report form. The actual assignment of the bleeding grades will occur at the DCC by a computerized algorithm programmed to evaluate the data from the case report forms.

6.4.1 Purpose of Adjudication

The role of the adjudication panel is to assess whether bleeding was a contributory cause of a patient's death. A key secondary endpoint of this trial is grade of bleeding, and "death due to bleeding" is one way of reaching Grade 4 bleeding.

6.4.2 Selection of Subjects for Adjudication

In accordance with the Platelet Dose Protocol, adjudication will be carried out for all patients who die on study and have either:

- Bleeding judged to be a possible, probable or definite contributory cause of death according to the patient's physician
- Grade 3 or 4 bleeding, or
- A situation where Grade 3 or 4 bleeding can not be ruled out due to missing data.

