4.3 Masking of Treatment Allocation

Treatment allocation will be masked. At enrollment, the patient's height and weight will be entered into the data management system. The computer will randomize the patient and the transfusion service staff at the trial site will be given the target platelet dose and acceptable dose range for the patient, but not the treatment arm the patient is assigned to. Although it is possible that the hospital staff caring for the patient, or the research staff performing the daily bleeding assessments, may be able to guess a patient's dose assignment based on the volume of platelets transfused, as well as the pre- and post-transfusion platelet counts, neither the hospital, research staff or transfusion service will be informed of a patient's randomization assignment.

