6.4.4 Adjudication Process

The DCC will prepare a packet of materials to be express mailed to members of the panel. The packet will include: a summary of the patient's demographic information, diagnoses, and bleeding grade history. Before sending the materials, the DCC will remove any information that could identify the patient or disclose the treatment group assignment. The panel may request additional information including hospital records or autopsy reports. Panel members will complete Form P100 – Adjudication Form to indicate their conclusions. The P100 sheets will be sent to the DCC for entry into the data management system. If all panel members agree as to whether bleeding was a cause of death, no further action will be taken. If the panel members do not agree, a conference call will be scheduled to resolve the adjudication.

A summary of the panel's findings will be presented to the DSMB during their semiannual meetings.

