7.3.1 Continuous Monitoring of Serious Adverse Events

Serious adverse events, including death of a subject participating in the Platelet Dose Protocol, must be reported to the DCC within 24 hours by phone or email. The Serious Adverse Event Form (Form P085) must be sent to the DCC via fax within 48 hours. The Serious Adverse Event Form will be entered into the Data Management System by the DCC. A summary of the adverse event must be submitted to the DCC within 10 days of the event. This category of events includes, but is not limited to, transient ischemic attack, myocardial infarction, stroke, Graft-versus-Host disease, venocclusive disease of the liver, seizure, TRALI, and death. It also includes other life-threatening and fatal (Grade 4 and 5) adverse events related to transfusion of blood products. These include life-threatening and fatal events related to allergic reaction/hypersensitivity, sinus bradycardia, sinus tachycardia, hypertension, hypotension, dyspnea, hypoxia, wheezing, cough, hemolysis, fever, and infection.

The DCC Medical Monitor assigned to the study will review all serious adverse events as data arrive at the DCC. In particular, the Medical Monitor will review the attributions listed on Form P085 regarding the relationships between the adverse event and transfusion, underlying disease and bleeding (unrelated, unlikely, possible, probable or definite). If an adverse event is reported on Form P085 as probably or definitely related to transfusion or bleeding, if the Medical Monitor thinks such an attribution might be warranted, or if other questions arise, the Medical Monitor will confer with a second non-study physician with expertise in transfusion medicine. In addition, each month these physicians will review together the attributions for serious adverse events that were not considered probably or definitely related to transfusion or bleeding.

The DCC will report all serious adverse events to the NHLBI Project Officer as described in the TMH MOP. Serious adverse events that are considered probably or definitely related to transfusion or bleeding (either on Form P085 or according to the Medical Monitor) will be flagged for special attention. In these cases, the Executive Secretary will contact the DSMB Chair to ask for advice on how to proceed.

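### A death with complete data and no Grade 3-4 bleeding reaches the masked panel only if a treating physician, who may have guessed the dose, thinks bleeding possibly contributed

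*Protocol*

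**What the plan says.** Not every death is adjudicated. Protocol section 6.4.2 says that "adjudication will be carried out for all patients who die on study and have either" one of three features:

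1. "Bleeding judged to be a possible, probable or definite contributory cause of death according to the patient's physician";
2. Grade 3 or 4 bleeding;
3. "A situation where Grade 3 or 4 bleeding can not be ruled out due to missing data".

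Grades come from a computer algorithm run at the DCC on case report form data (section 6.4). Section 6.4.1 gives the panel the question of whether bleeding contributed to death, and notes that a bleeding death is one route to Grade 4.

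On masking, section 4.3 says that hospital, research and transfusion service staff are not told the assignment. It also accepts a limit to this: "the hospital staff caring for the patient, or the research staff performing the daily bleeding assessments, may be able to guess a patient's dose". The clues it names are platelet volumes and counts. Section 6.4.4 has the DCC strip the panel's materials of anything that reveals the arm.

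On the packet, section 6.4.4 says: "The packet will include: a summary of the patient's demographic information, diagnoses, and bleeding grade history". The panel may ask for more, including hospital records and autopsy reports. Section 7.3.1, on serious adverse events including death, says: "A summary of the adverse event must be submitted to the DCC within 10 days of the event".

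**The concern.** The panel is masked, but one of the routes to it runs through the opinion of someone who may have inferred the dose. For a death with complete data and no Grade 3-4 bleeding, it is the only route. If belief about the dose affects how readily a physician names bleeding as a possible contributor, referral could differ by arm, in either direction. The panel cannot correct a case that it never sees.

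Two outcomes are exposed. Death due to bleeding is secondary endpoint 15a, compared pairwise at each scheduled DSMB meeting with the Table 5 boundaries as guidelines (section 7.4.2). A death judged due to bleeding also counts as Grade 4 in highest grade of bleeding, one of the key secondary endpoints tested at the .017 level (section 8.1). Uneven referral could create a small spurious difference, or hide part of a real one from a DSMB that weighs observed rates as well as boundaries (section 7.4).

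**Working it through.** The protocol states no figure for this point, so there is none to reproduce. The check is first a reading of the text and then an illustration on assumed rates.

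**Which deaths depend on the physician alone?** Going through the three routes in section 6.4.2:

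| Death on study | Route to the panel |
|---|---|
| Grade 3-4 bleeding recorded | Automatic, through the DCC algorithm |
| Grade 3-4 status unresolved because of missing data | Automatic |
| Complete data, highest grade 2 or below | Physician's opinion only (possible contribution is enough) |

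**Can a contributory bleed fall in the last row?** In Table 2, the only Grade 3 criterion in the oral/nasal, skin, gastrointestinal, genitourinary, pulmonary and invasive-site rows is red cell transfusion beyond routine needs. The footnote ties that transfusion to treatment of the bleeding within 24 hours of onset. Both hemodynamic-instability criteria (Grades 3 and 4) also require extra red cells. CNS bleeding reaches Grade 3 or 4 only through imaging, lumbar puncture or retinal findings. So a lung or airway bleed in a patient who dies before extra red cells are given, or an intracranial bleed never imaged, can remain at Grade 2 or below. It would become Grade 4 only as fatal bleeding, which turns on the panel. Imaging is not a scheduled assessment in section 6.1, so it is unclear whether its absence counts as missing data.

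**How large could the uneven loss be?** The 1,350 patients (450 per arm) come from section 8.2. Everything else here is an assumption.

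| Step | Low | High |
|---|---|---|
| On-study mortality 2% to 5% | 1,350 × 0.02 = 27 | 1,350 × 0.05 = 67.5 |
| No Grade 3-4 bleed, 30% to 60% | 27 × 0.3 = 8.1 | 67.5 × 0.6 = 40.5 |
| Bleeding contributed, 10% to 20% | 8.1 × 0.1 = 0.81 | 40.5 × 0.2 = 8.1 |
| Per arm (÷ 3) | 0.27 | 2.7 |
| Referral 90% in one arm, 60% in another (× 0.3) | 0.08 | 0.81 |

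The difference is thus about 0.1 to 0.8 death per arm.

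**Wider sensitivity range.** Let q be the true bleeding-death rate, equal in both arms; s the share reachable only through the physician; and r the chance of referral. The counted rate is q × (1 − s + s × r), so two arms differ by q × s × (r₁ − r₂).

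- Mild: q = 1%, s = 10%, r = 0.9 against 0.6. Difference 0.01 × 0.1 × 0.3 = 0.03 percentage points, or 4.46 against 4.32 counted deaths in 450.
- Deliberately extreme: q = 3%, s = 50%, r = 0.9 against 0.3. Difference 0.03 × 0.5 × 0.6 = 0.9 points, or 12.8 against 8.8 counted deaths.

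The extreme case implies 3 × 450 × 0.03 = 40.5 bleeding deaths in the trial, which is 60% of even the higher assumed total of 67.5 deaths. Rounded to 13 against 9, it gives a Fisher exact p of 0.52, far from the final boundary of 0.0155.

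**With every death referred,** r = 1 in all arms and the difference is zero by construction.

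**The case against.** The strongest case against is that the residue is narrow and partly guarded.

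- The bar for physician referral is low, and the missing-data route bypasses the physician. Both limit the gap; neither closes it.
- Several Grade 3-4 criteria need no extra red cells: CNS bleeding on imaging, retinal bleeding with visual impairment, CNS symptoms with a non-traumatic bloody lumbar puncture, and body-cavity bleeding with organ dysfunction or intervention. This stands, and it is why the group is small.
- Under section 7.3.1 the Medical Monitor reviews every serious adverse event for attribution to bleeding, and confers with a second, non-study physician where that attribution might be warranted. Each month the two also review events not rated probably or definitely related to transfusion or bleeding. This is a real independent check on the opinion at issue. Its stated outcome, however, is flagging to NHLBI and advice from the DSMB Chair; no referral to the panel is described.
- All-cause mortality is monitored without any referral step, and endpoint 15a is only descriptive at the final analysis (section 8.1). Both stand.

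A reader might infer more than the text supports:

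- That treating physicians are unmasked. Section 4.3 says they are not informed, only that they may guess.
- That the panel merely echoes the grade history, because the listed packet says nothing about the death and "If all panel members agree as to whether bleeding was a cause of death, no further action will be taken". The list may not be exhaustive and the panel may request records, so this is conjecture.
- That records requested later arrive unredacted. Section 6.4.4 is silent on this, and silence does not show it.
- That the loss is as large as the endpoint itself. The protocol gives no bleeding-death rate against which to judge that.

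**Conclusion.** The gap is real but narrow. It is a weak point in the selection rule, not an error or contradiction. For deaths with complete data and no Grade 3-4 bleeding, entry to masked adjudication rests on the judgement of a physician who may have guessed the dose, and no stated route lets the independent attribution review supply the missed case.

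The size rests wholly on assumed mortality, bleeding contribution and referral rates. On the main assumptions it is below about one death per arm. A difference near four deaths needs the extreme combination shown above, and even that would not approach a Table 5 boundary. The primary endpoint changes only for a patient with no recorded Grade 2 bleeding before a bleeding death that was missed. Sample size, power and alpha are unaffected. This is a minor point, worth acting on because the remedy is cheap and removes the selection step completely.

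**What to change.** In section 6.4.2, refer every on-study death to the existing masked panel, whatever the physician's opinion or the bleeding grade. In section 6.4.4, add to every packet the adverse event summary that the DCC already receives under section 7.3.1, with anything that could reveal the dose removed. It would also help to state that the same removal applies to hospital records the panel requests later; that is a clarification only.

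The cost is protocol and adjudication wording, DCC redaction time and some extra packets at the six-monthly reviews already scheduled in section 6.4.5. On the assumptions above, the deaths without Grade 3-4 bleeding number about 8 to 41 over the whole trial. That is an upper limit on the added packets, since some of these deaths would be referred anyway.
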